#### 12.4 Data Transmission from Sponsor

NA

#### 12.5 Study Monitoring Plan

Monitoring activities will be conducted according to ZOLL's Monitoring of Clinical Studies Standard Operating Procedure (ZOLL 90D0013) and will be documented.

#### 13 Risks and Benefits

The  $\mu$ Cor system is a non-significant risk, noninvasive medical monitoring device. The potential risks from wearing the device may include discomfort, skin irritation, itching, rash, contact dermatitis, or breaching of skin if the patch adhesive is the removed too quickly. The  $\mu$ Cor system has not been tested for compatibility with magnetic resonance imaging machines and external defibrillators.

No benefits to participation in this study are anticipated for subjects participating in phase I portion of the study. For subjects participating in phase II portion of the study, the  $\mu$ Cor system may help to detect abnormal heart rhythms in a timely manner and thus prompting a suitable treatment.

#### 14 Ethical Considerations

This study is to be conducted according to US and international standards of Good Clinical Practice (FDA Title 21 part 312 and International Conference on Harmonization guidelines), applicable government regulations and Institutional research policies and procedures.

This protocol and any amendments will be submitted to a properly constituted independent Ethics Committee (EC) or Institutional Review Board (IRB), in agreement with local legal prescriptions, for formal approval of the study conduct. The decision of the EC/IRB concerning the conduct of the study will be made in writing to the investigator and a copy of this decision will be provided to the sponsor before commencement of this study. The investigator should provide a list of EC/IRB members and their affiliate to the sponsor.

#### 14.1 Subject Consent and Confidentiality

All subjects for this study will be provided a consent form describing this study and providing sufficient information for subjects to make an informed decision about their participation in this study. See Documents 90D0167\_ICD for a copy of the Subject Informed Consent Form. This consent form will be submitted with the protocol for review and approval by the EC/IRB for the study. The formal consent of a subject, using the EC/IRB-approved consent form, must be obtained before that subject undergoes any study procedure. The consent form must be signed by the subject or legally acceptable surrogate, and the investigator-designated research professional obtaining the consent.

Each subject will receive a unique subject identification number. The subject's name and identity will be known to the local principal investigator and the Sponsor, as necessary for device use and study conduct, but will be kept confidential. Authorized personnel from the IRB and regulatory authorities may have access to original subject records.

At the end of the data collection period, a fully de-identified, HIPAA-compliant dataset will be created using all variables available from the Case Report Forms and device data contained within LifeVest network. This dataset will be used for analysis and publication purposes.

In the event that a subject revokes authorization to collect or use Protected Health Information (PHI), the investigator, by regulation, retains the ability to use all information collected prior to the revocation of subject authorization. For subjects that have revoked authorization to collect or use PHI, attempts should be made to obtain permission to collect at least vital status (i.e. that the subject is alive) at the end of their scheduled study period.

#### 14.2 Subject Financial Responsibility and Stipends

There is no cost to the patient to participate in this research study. The sponsor will cover the cost of the device. The cost of a subject's ongoing medical care will remain the responsibility of his/her insurance.

#### 15 Publication Plan

#### 15.1 Authorship

The publication committee will consist of the following members:

- 1. The sponsor's Vice President of Medical and Clinical Affairs and/ or their representatives, up to three individuals in total.
- 2. A minimum of 3 physician investigators will be chosen by the sponsor using the following criteria:

Page 23 of 27

ZOLL Document Number: 90D0167 PATCH Feasibility Study

Version: C

- A. Contribution to study design
- B. Contribution to patient enrollment
- C. Contribution to data analysis
- D. Contribution to manuscript preparation

The publication committee will then chose authors based on the above criteria. The publication committee will decide on the publication strategy, including all sub-studies and other presentations. Physicians on the publication committee can serve as authors. No employees of the sponsor will serve as authors. The authors agree that any proposed publication relating to the research conducted under this protocol will be submitted to the sponsor for review at least forty five (45) days prior to submission for publication. Upon notice by the sponsor during this period that any of sponsor's confidential information is contained in the publication(s) and/or intellectual property considerations apply, the publication may be delayed for an additional period of up to ninety (90) days (for intellectual property considerations) or until all confidential information has been eliminated from the publication(s) and sponsor has approved the publication. It may be determined by the sponsor that no data from this study will be published.

#### 15.2 Data ownership

Data resulting from this study are the property of the sponsor, with each site having coownership with sponsor of the data generated within their site. The sponsor may make copies of all documents and reports related to the study at sponsor's expense, and all sites will maintain and retain study records for a period of ten (10) years following the termination of the study. The sponsor shall have access to all such records during this period with adequate prior notice and during normal business hours.

#### 16 List of Abbreviations

ECG – Electrocardiograph

HF – Heart Failure

MCT – Mobile Cardiac Telemetry

RF – Radio Frequency

# 18 Appendix A

# **Subject Diary**

Page 25 of 27

Version: C

DATE Sur	Mon	Tue	Wed	Thu Fri S	a t
----------	-----	-----	-----	-----------	------------

# Daily activities

Please circle the level of activity for each time slot. If applicable, you should add additional detail. For example: "I watched television from 10:30 am - 11:30 am" or "I walked around the mall from 01:45 pm - 02:30 pm"

morning	Circle your activity level.			
	Active	Sitting	Sleeping	
00:00 – 02:00	Details:			
	Active	Sitting	Sleeping	
02:00 – 04:00	Details:			
	Active	Sitting	Sleeping	
04:00 – 06:00	Details:			
	Active	Sitting	Sleeping	
06:00 – 08:00	Details:			
	Active	Sitting	Sleeping	
08:00 –10:00	Details:			
	Active	Sitting	Sleeping	
10:00 –12:00	Details:			

evening	Circle your activity level.			
	_			
12:00 – 14:00	Active	Sitting	Sleeping	
12.00	Details:			
14:00 – 16:00	Active	Sitting	Sleeping	
14.00 – 16.00	Details:			
40.00 40.55	Active	Sitting	Sleeping	
16:00 – 18:00	Details:			
18:00 – 20:00	Active	Sitting	Sleeping	
10.00 20.00	Details:			
20:00 – 22:00	Active	Sitting	Sleeping	
20.00 - 22.00	Details:			
22:00 – 24:00	Active	Sitting	Sleeping	
22.00 – 24.00	Details:			

# **Symptoms**

Please circle any of the following symptoms that you are experiencing. If possible, note the time when the symptoms started and duration.

Racing heartbeat	Slow heartbeat	Flutter in yo	ur chest	Chest pain	
Shortness of breath	Lightheadedness o	r dizziness	Sweating	Near fainting	Time:
Fatigue Swelling	of feet, ankles, legs,	or abdomen	Other:		Duration:
Racing heartbeat	Slow heartbeat	Flutter in yo	ur chest	Chest pain	
Shortness of breath	Lightheadedness o	r dizziness	Sweating	Near fainting	Time:
Fatigue Swelling	of feet, ankles, legs,	or abdomen	Other:		Duration:
Racing heartbeat	Slow heartbeat	Flutter in yo	ur chest	Chest pain	
Shortness of breath	Lightheadedness o	r dizziness	Sweating	Near fainting	Time:
Fatigue Swelling	of feet, ankles, legs,	or abdomen	Other:		Duration:
	-				

ZOLL Document Number: 90D0167 PATCH Feasibility Study

area

Page 26 of 27

Version: C

[figure not shown]
DATE		Sun Mon Tue Wed Thu Fri Sat	
Skin Con	dition rea	ease rate the skin condition under the $\mu$ Cor patch adhesive. Do this be applying the new patch. Provide the skin condition rating for each device location) that you are wearing.	
		Front Location	
Date and	I Time of patch re	eplacement:	
Please ra	ate the skin cond	ition in the following manner:	
1. G	Grade 0 (None): N	lo redness, rash, irritation, or itchiness	
2. G	Grade 1 (Mild): Re	edness	
	Ra	ish	
	Irri	tation	
	Itc	hiness	
	Grade 2 (Moderat eeling/scaling	e): Rash that breaks skin, hard or soft pimples or light	
	Grade 3 (Severe): rea	Blistering, open ulcers, wet peeling, serious rash over a la	arge
		Side Location	
Date and	I Time of patch re	eplacement:	
Please ra	ate the skin cond	ition in the following manner:	
1. G	Grade 0 (None): N	lo redness, rash, irritation, or itchiness	
5. G	Grade 1 (Mild): Re	edness	
	Ra	sh	
	Irri	tation	
	Itc	hiness	
	Grade 2 (Moderat eeling/scaling	e): Rash that breaks skin, hard or soft pimples or light	

3. Grade 3 (Severe): Blistering, open ulcers, wet peeling, serious rash over a large

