#### 2 Study Objectives

#### 2.1 Primary Objective(s)

The primary objective of this study is to observe the feasibility of the novel  $\mu$ Cor system to remotely monitor patients. Feasibility will be assessed in terms of:

- 2.1.1 Logistics of equipping patients with the  $\mu$ Cor system in the physician's office. This will include verifying that the system is able to transmit data to a remote server and that a monitoring report is received by the physician's office.
- 2.1.2 Subject's ability to wear the device for the specified time period of up to 90 days.
- 2.1.3 Subject's ability to place the device in the correct anatomical position during every reapplication, as described in the patient instructions for use. Device placement case report forms and daily device data signal quality will be used to track the accuracy of device placement and repeatability.
- 2.1.4 Ability of the system to transmit data daily to the remote servers for processing.
- 2.1.5 Ability to provide a timely arrhythmia monitoring (daily, episodic, and end of monitoring) reports to physicians.
- 2.1.6 Documenting the following clinically actionable events in an outpatient setting via weekly phone calls to the subject:
  - 2.1.6.1 Emergency room visits
  - 2.1.6.2 Unplanned physician visits
  - 2.1.6.3 New arrhythmia and heart failure (HF) symptoms
  - 2.1.6.4 All-cause and HF hospitalizations
  - 2.1.6.5 Alterations and additions in HF and cardiac medications
  - 2.1.6.6 All-cause and cardiovascular mortality at 90 days

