#### 6.2.2 Visit 2: Wear period from 0 to 7 days

Subjects will wear two µCor devices for the first 7 days. All subjects will keep a diary to record their daily activities of living, their skin condition due to use of the µCor device/s, and the placement location of the device (Appendix A). For subjects participating in phase II of the study they will keep a dairy to record any symptoms related to heart rhythm abnormalities and heart failure (Appendix A). Symptoms associated with transient arrhythmias include syncope, near syncope, dizziness, palpitation, shortness of breath, chest discomfort, weakness, and diaphoresis. Symptoms of heart failure include: dyspnea, fatigue and weakness, edema, persistent coughing or wheezing, lack of appetite and nausea, confusion and impaired thinking, and increased heart rate. Arrhythmia monitoring reports will be provided to the physician when an actionable arrhythmia is detected per the notification specified by the physician-investigator. On day 7, the study coordinator will call the subjects to record any clinical actionable events and check on status of the device. During the call, subjects will be requested to send to send their dairy every week to the study coordinator. In addition, the study coordinator will remind the subjects to remove one of the devices, midaxillary or midclavicular, depending on whether the subjects are assigned an odd or even number. Subjects will also be instructed on how to send one of the study devices back to the sponsor.

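### The diary's circle list has no entry for 5 of the 14 symptoms named in 6.2.2, so these may be recorded less completely, and with less timing detail, than the rest

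*Combined protocol and SAP*

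**What the plan says.** Section 6.2.2 states that phase II subjects keep a diary "to record any symptoms related to heart rhythm abnormalities and heart failure (Appendix A"), and then gives two lists. For arrhythmia: "Symptoms associated with transient arrhythmias include syncope, near syncope, dizziness, palpitation, shortness of breath, chest discomfort, weakness, and diaphoresis". For heart failure: "Symptoms of heart failure include: dyspnea, fatigue and weakness, edema, persistent coughing or wheezing, lack of appetite and nausea, confusion and impaired thinking", with increased heart rate as the last entry.

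The Symptoms page of Appendix A opens with "Please circle any of the following symptoms that you are experiencing" and asks for the time and duration of each symptom where possible. Each of its three identical blocks prints ten items and a free-text field labelled Other.

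Section 2.1.6 makes the weekly calls the route for the related study data: "Documenting the following clinically actionable events in an outpatient setting via weekly phone calls to the subject". New arrhythmia and heart-failure symptoms are item 2.1.6.3 on that list. Objectives 2.2.2 and 2.2.3 relate clinically actionable events to detected rhythm abnormalities and to changes in thoracic fluid content. Sections 8.3 and 8.4 provide for descriptive and qualitative analysis without predefined acceptance criteria.

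**The concern.** The form and the section that prescribes it do not cover the same symptoms. A subject who faints can circle "Near fainting" but has nothing to circle for the faint itself, although syncope is the first arrhythmia symptom in 6.2.2. Cough or wheeze, appetite loss or nausea, and confusion are likewise named in 6.2.2 and absent from the circle list.

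What is at stake is even ascertainment. A printed symptom is put in front of the subject on every diary page. An unprinted one must be thought of and written in, or remembered when the coordinator calls. If the two groups are captured differently, the symptom record under 2.1.6.3 partly reflects the layout of the form, and so does one side of the comparisons in 2.2.2 and 2.2.3. This cannot be put right once the diaries have been collected.

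**Working it through.** There is no figure in the plan to reproduce. The check is an item-by-item comparison of 6.2.2 with the Symptoms page of Appendix A.

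**Matching, accepting synonyms**

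| Symptom in 6.2.2 | List in 6.2.2 | Printed diary item | Match |
|---|---|---|---|
| Syncope | arrhythmia | none | no |
| Near syncope | arrhythmia | near fainting | yes |
| Dizziness | arrhythmia | lightheadedness or dizziness | yes |
| Palpitation | arrhythmia | racing heartbeat; flutter | yes |
| Shortness of breath / dyspnea | both | shortness of breath | yes |
| Chest discomfort | arrhythmia | chest pain | yes |
| Weakness | both | none (fatigue is nearest) | no |
| Diaphoresis | arrhythmia | sweating | yes |
| Fatigue | heart failure | fatigue | yes |
| Edema | heart failure | swelling | yes |
| Cough or wheeze | heart failure | none | no |
| Appetite loss or nausea | heart failure | none | no |
| Confusion or impaired thinking | heart failure | none | no |
| Increased heart rate | heart failure | racing heartbeat | yes |

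**Counting**

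- The arrhythmia list has 8 entries. The heart-failure list has 7, or 8 once fatigue and weakness are separated.
- Distinct symptoms: 8 + 8 = 16, less 2 that appear in both lists (shortness of breath and weakness), gives 14.
- Entries with no printed option: 2 of 8 for arrhythmia (syncope, weakness) and 4 of 8 for heart failure (weakness, cough or wheeze, appetite or nausea, confusion). 2 + 4 = 6, less weakness counted twice, gives 5.
- Result: 5 of 14 unmatched (5/14 = 36%) and 9 of 14 matched.

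**Sensitivity to the matching.** If fatigue is taken to cover weakness, 4 of 14 remain (29%). If near fainting is also taken to cover syncope, 3 of 14 remain (21%), all from the heart-failure list. The mismatch does not depend on strict reading of terms.

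**In the other direction.** Slow heartbeat is printed in the diary but not named in 6.2.2.

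**How an unlisted symptom can still be recorded**

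- *Other field in the diary.* It is present in every block, beside the time and duration fields, so a write-in can be timed. It depends on the subject thinking of the symptom. The protocol gives no rule for coding write-ins to the 6.2.2 terms, and 8.6 on missing data is marked not applicable.
- *Weekly call.* This is the designated route for 2.1.6.3. The protocol text gives no symptom prompts for the call. The case report forms are a separate document that was not available, so prompts may exist there. Recall can span up to seven days, and the protocol does not say that time or duration is asked.
- *Patient trigger on the sensor (1.4.1).* It is open to any symptom, but the three examples given (palpitations, shortness of breath, lightheadedness) all have a circle option already.

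Every unlisted symptom therefore has a route into the data. None of the routes described in the protocol prompts for it by name.

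**The case against.** The strongest reply is that the diary is not the stated source for the endpoint. Section 2.1.6 puts new arrhythmia and heart-failure symptoms on the weekly calls, and 6.2.2 to 6.2.4 repeat that coordinators record actionable events there. There are also office visits at days 30, 60 and 90, and unscheduled visits. A faint serious enough to lead to an emergency visit, an unplanned physician visit or a hospitalization is recorded as an event in its own right. This stands: a symptom missing from the diary is not thereby missing from the study. A reader might infer from the mismatch that the five symptoms will be under-recorded, but the documents do not support a certainty.

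A reader might also want to put a percentage on the loss. Any such figure would only be the complement of an assumed capture rate for the free-text field, and the documents contain nothing to inform that rate.

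Nor do the documents show that the gap chiefly damages the thoracic-fluid objective (2.2.3). Three of the five symptoms are on the heart-failure list only, but shortness of breath, swelling and fatigue are all printed. Phase II eligibility requires an indication for outpatient cardiac monitoring, not heart failure, so the number of heart-failure episodes at stake is unknown.

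Finally, 6.2.2 says that symptoms include those listed, which is illustrative wording, and a short plain-language list with a write-in field is a legitimate form design. That explains why the form need not reproduce every term. It does not explain printing near fainting without fainting, or adding slow heartbeat while leaving out five symptoms that the protocol itself chose to name.

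**Conclusion.** The mismatch is real: 5 of the 14 distinct symptoms in 6.2.2 have no circle option in Appendix A. Those five may be recorded less completely than the printed ones, and with less information on timing when they surface only at the weekly call. This rests on one assumption, stated as such: that symptoms a subject is not prompted for are reported less reliably than those put in front of them. The size of any loss cannot be estimated from the documents.

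The consequence is modest. The study has up to 44 phase II patients chosen by convenience, descriptive analysis and no acceptance criteria, so no test or decision rule turns on symptom counts. The change is still worth making, because uneven capture cannot be corrected afterwards and the remedy costs very little.

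**What to change.** Add fainting, weakness, cough or wheeze, loss of appetite or nausea, and confusion to the circle list in each block of the Appendix A Symptoms page, so that the form covers every symptom in 6.2.2. Keep the Other field. Use the same list as prompts on the weekly calls, so that both routes ask about the same symptoms.

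The cost is one revised diary page with five more items to scan, and a short prompt list for coordinators. No visit, sample size or analysis changes.

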# **Patch Location**

Please outline the  $\mu$ Cor patch location for each device that you are wearing.

#### **Front Location**

#### **Side Location**
